### 299 **Primary hypothesis sample size considerations**

300 The primary study hypothesis is that TRG strategy is superior to CG strategy resulting in a  
301 larger percent of DAOH. Because possible follow-up varies between patients (12 to 24 months after  
302 the 9-week training period), the primary analysis will rely on the percent of DAOH calculated as the  
303 ratio of the DAOH divided by total days of follow-up for each patient.

304 The sample size for this study is calculated assuming 1:1 treatment allocation ratio, and an  
305 overall two-sided level of significance  $\alpha = 0.05$ . Mean difference in the number of DAOH for the  
306 TRG arm and the CG arm is 21 days with a common standard deviation in each arm of 100. The  
307 Wilcoxon-Mann-Whitney test with the above assumptions and with a sample size of 400 evaluable  
308 subjects per study arm (a total of 800) yields 80% power to declare the observed difference as  
309 statistically significant. Accounting for a 5% loss to the follow-up, the total number increases to 842.

310

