### 311 **Statistical Analyses**

#### 312 Primary Outcome

313 The primary analysis will be based on the percent of DAOH during the 12-24-month follow-  
314 up and analyzed using the Wilcoxon-Mann-Whitney test. DAOH is defined as the number days out of  
315 the first 365 days of follow-up that the patient was alive minus the total number of days the patient  
316 spent in the hospital (sum of days spent in the hospital for each hospitalization). Fractions of days  
317 spent in the hospital will be rounded up to full days. We plan to conduct two analyses, intent-to-treat  
318 (ITT) and modified intent-to-treat (MITT). The follow-up for ITT will start at randomization and  
319 extend for a minimum of about 14 months (9 week training period and 12 month follow-up) and a

320 maximum of 26 months (9 week training period plus 24 months of follow-up). For the MITT analysis,  
321 the follow-up will start at the end of the 9-week period.

322

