### 323 Missing data

324 If a patient remained in the study for less than 365 days for reasons other than death, the  
325 following imputation methods will be applied:

- 326 1. Proportional Fraction. The proportion of DAOH will be calculated for the period the patient  
327 was on study and multiplied by 365;
- 328 2. Worst case scenario. Days not on study will be counted as NOT alive/out of hospital;
- 329 3. Best case scenario. Days not on study will be counted as alive and out of hospital.

330

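### The percent-DAOH formula gives no denominator for patients who die, and its 365-day numerator does not match a denominator of about 14 to 26 months

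*Protocol*

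**What the plan says.** Four parts of the protocol bear on the formula.

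- **Primary hypothesis sample size considerations** gives the reason for using a ratio: "Because possible follow-up varies between patients (12 to 24 months after" the training period). It then defines percent DAOH as the "ratio of the DAOH divided by total days of follow-up for each patient". No rule is given for a patient who dies.
- **Statistical Analyses, Primary Outcome** names a 12–24-month window for the percentage, but counts DAOH from "the first 365 days of follow-up that the patient was alive minus the total number of days the patient" spent in hospital. Intention-to-treat (ITT) follow-up starts at randomization and lasts from about 14 to 26 months. Modified ITT (MITT) follow-up starts after the 9-week period.
- **Missing data** offers three imputation rules (proportional, worst case, best case), all conditional on this: "If a patient remained in the study for less than 365 days for reasons other than death". All three work on a 365-day base.
- **Table 7** again gives the primary endpoint as a percentage over 12–24 months.

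**The concern.** A DAOH endpoint penalises death because days after death are lost from the numerator while the denominator stays fixed. That works only if the denominator does not shrink with the patient's survival. Total follow-up for a patient can naturally be read as the time that patient was actually followed, which would end at death. The Missing data section supports that reading to a degree, since its wording treats death as one way of being in the study for under 365 days. A programmer who coded date of death or last contact minus start date would not be contradicting the text. Death would then shorten numerator and denominator together.

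Taking the other reading does not rescue the formula, because the numerator stops at day 365 and the denominator does not. The primary endpoint of an open-label trial would be left to a choice between readings that rank the same patients very differently.

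**Working it through.** **Inputs from the protocol.** The training period is 9 weeks = 63 days, followed by 12 to 24 months, taken as 365 to 730 days. The ITT window is 63 + 365 = 428 to 63 + 730 = 793 days. The MITT window is 365 to 730 days.

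**The plan's own figure.** With a difference of 21 days, SD 100, two-sided 0.05 and 80% power, the two-sample formula gives 2 × [100 × (1.960 + 0.842)/21]² ≈ 356 per arm. Dividing by the relative efficiency of the Wilcoxon-Mann-Whitney test gives 373 (normal data, 0.955) or 412 (lower bound, 0.864). At 400 per arm the power is 82.7% or 78.8% respectively, so the stated 400 is reasonable. Also, 800/0.95 = 842.1, against 842 stated. The calculation is in days, so it does not depend on the denominator and does not settle it.

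**Step 1: death on day d with no hospital days (ITT).**

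| Day of death | Observed follow-up, d/d | d/365 | d/428 | d/793 |
|---|---|---|---|---|
| 60 | 100% | 16.4% | 14.0% | 7.6% |
| 100 | 100% | 27.4% | 23.4% | 12.6% |
| 180 | 100% | 49.3% | 42.1% | 22.7% |
| 300 | 100% | 82.2% | 70.1% | 37.8% |

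A death on day 100 after a 20-day stay scores 80/100 = 80% on observed follow-up, against 80/428 = 18.7% or 80/793 = 10.1%. The hospital days count on either reading. The days lost to death count only on the second.

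**Step 2: survivor never admitted, numerator limited to 365 days.**

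- ITT: 365/428 = 85.3% with the shortest follow-up and 365/793 = 46.0% with the longest.
- MITT: 365/365 = 100% and 365/730 = 50%.

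These patients have the same, best possible outcome, and the score reflects only length of follow-up. Ranks can also invert. With potential follow-up as denominator, an unadmitted patient who dies on day 300 of a 428-day window scores 70.1%, above the 46.0% of a never-admitted survivor followed for 793 days. With observed follow-up as denominator, that death scores 100%, above the ITT maximum of 85.3% for anyone who completes follow-up alive.

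**Step 3: illustration on assumed rates.** Assumptions: 425 per arm, follow-up uniform on 428–793 days, 0.7 admissions per year in both arms, mean stay 8 days, DAOH counted over all follow-up (so without the 365-day limit), 1,000 simulated trials per row.

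| 14-month mortality (TR vs control) | Rejects, observed follow-up | Rejects, potential follow-up | Mean difference, observed / potential |
|---|---|---|---|
| 8% vs 8% | 5.0% | 5.5% | 0.0 / 0.0 points |
| 5% vs 15% | 13% | 92% | 0.0 / 7.1 points |
| 8% vs 16% | 8% | 77% | 0.0 / 5.6 points |

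A second set of assumptions (400 per arm, 0.8 admissions per year, mean stay 9 days, 12-month mortality 8% with TR vs 15% in control) gave about 75% power in favour of TR with potential follow-up and under 1% with observed follow-up. On observed follow-up, about 8–10% of those trials were significant against TR, because longer survivors have more time to be admitted.

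**The case against.** The strongest reply is that no part of the protocol says follow-up ends at death, and that the surrounding text points the other way. The ratio is introduced because possible follow-up differs between patients, which concerns calendar availability and not survival. A minimum ITT follow-up of about 14 months could not hold if death ended follow-up. Counting days alive out of a fixed number of days is the usual way to penalise death. Leaving deaths out of imputation is also what one would do if days after death were already known to count as zero, and the proportional rescaling is withheld from them. All of this stands as evidence of likely intent.

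A reader might therefore infer too much in the other direction: that the protocol removes deaths from the primary endpoint and the trial cannot answer its question. The documents do not support that. It is one reading of an undefined term. Even on that reading a death after hospital days scores below 100%, and all-cause and cardiovascular mortality are compared separately by Cox regression.

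The simulations carry limited weight as well. Equal admission rates in both arms mean that only mortality can separate the arms, so the loss of power with a truncated denominator is largely built in.

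Two things survive the reply. Intent inferred from context does not define a primary endpoint. And if potential follow-up is intended, the mismatch with the 365-day numerator remains. Randomization should balance length of follow-up between arms, so that mismatch is mainly a source of noise and misranking and not of systematic bias, but the score is still not what its name says. A SAP may add derivation detail, but the protocol itself fixes this formula, and its parts conflict.

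**Conclusion.** The concern holds in this form: the percent-DAOH formula is not sound as written. The denominator is undefined for patients who die, and the numerator and denominator cover different windows.

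- If observed follow-up is used, an unadmitted day-100 death scores 100% instead of 23% or 13%, and time lost to death is not penalised.
- If potential follow-up is used with the present numerator, never-admitted survivors range from 85% down to 46% for no clinical reason.

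These figures are arithmetic on the protocol's own windows and assume only 365-day years and a 63-day training period. The power figures show that the choice of reading can matter greatly when mortality differs between arms. They do not estimate this trial's power, because the protocol gives no mortality, admission or length-of-stay rates. The formula should be settled before any comparison by arm.

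**What to change.** Replace the definition in the sample size section and in Primary Outcome with one formula: percent DAOH = 100 × (days in the window alive and out of hospital) / (days in the window). Then:

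- Choose one window for both parts: either the first 365 days for everyone, or time zero to the patient's planned or administrative end of follow-up. State it for ITT and for MITT.
- State that days after death count as zero in the numerator and stay in the denominator.
- Subtract only hospital days that fall inside the window.
- Send only non-fatal loss to follow-up to the imputation rules. Those rules are written for 365 days, so if the longer window is chosen they must be restated for it; otherwise loss after day 365 has no rule.
- Bring Table 7 into line, and say which window the 21-day difference and SD of 100 refer to.

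The cost is a few sentences and a change to the derivation program. No new data are needed, and the stated sample size, being set in days, does not change through the denominator.

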### 311 **Statistical Analyses**

#### 312 Primary Outcome

313 The primary analysis will be based on the percent of DAOH during the 12-24-month follow-  
314 up and analyzed using the Wilcoxon-Mann-Whitney test. DAOH is defined as the number days out of  
315 the first 365 days of follow-up that the patient was alive minus the total number of days the patient  
316 spent in the hospital (sum of days spent in the hospital for each hospitalization). Fractions of days  
317 spent in the hospital will be rounded up to full days. We plan to conduct two analyses, intent-to-treat  
318 (ITT) and modified intent-to-treat (MITT). The follow-up for ITT will start at randomization and  
319 extend for a minimum of about 14 months (9 week training period and 12 month follow-up) and a

320 maximum of 26 months (9 week training period plus 24 months of follow-up). For the MITT analysis,  
321 the follow-up will start at the end of the 9-week period.

322

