#### 226 Education

227           Education program is designed and run by the TR team. Patients will be taught how to self-  
228 evaluate, how to measure HR, blood pressure, body mass, how to performed all modalities of exercise  
229 training, how to evaluate the level of perceived exertion according to the Borg scale and how to  
230 operate a TR set. Education will also encompass nutritional counselling, lipid management, smoking  
231 cessation, vocational and psychosocial support.

232

233 **Control Group**

234 Patients randomized to the CG will undergo baseline clinical examinations during a 3-day  
235 hospitalisation and then will be under observation until the end of the 9th week and will receive usual  
236 care appropriate for their clinical status and standardized within a particular center (some of them can  
237 participate in a rehabilitation program and some of them has remote monitoring of CIEDs). After the  
238 9th week patients will undergo final assessments during a 3-day hospitalization.

239 All patients, regardless of the treatment group, will receive recommendations for suitable  
240 lifestyle changes and self-management according to guidelines.

241

242 **Clinical examinations**

243 All 850 patients will undergo the following assessments at entry (during 5 days of  
244 hospitalization-TRG, and 3 days of hospitalisation-CG) and after completing the 9-week program  
245 (during 3 days hospitalisations – both groups): clinical examination with symptom evaluation (NYHA  
246 class), blood testing [blood count, serum creatinine, electrolytes (sodium, potassium), glycaemia, N-  
247 terminal pro B-type natriuretic peptide (NT-proBNP), aspartate aminotransferase, alanine  
248 aminotransferase, thyroid stimulating hormone (TSH), international normalized ratio (INR),  
249 urinalysis], ECG, two-dimensional echocardiography, six-minute walk test (6-MWT), CPET, 24 hours  
250 holter ECG monitoring, evaluation of CIEDs proper functioning, and psychological assessment: the  
251 QoL based on SF-36 Survey; the depression based on Beck inventory; the anxiety based on STAY.  
252 Additionally, after 9 weeks, the TRG will be analyzed for: safety and patients' acceptance of and  
253 adherence to hybrid comprehensive TR.

254

255 **Evaluation of novel model of hybrid comprehensive telerehabilitation in terms of tertiary**  
256 **analyses**

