### 336 Secondary Outcomes Assessed at 12 months.

337 The following time-to-event outcomes will be illustrated using Kaplan-Meier plots and  
338 compared between treatment arms using Cox proportional hazards regression with site and treatment  
339 arm as covariates: all-cause mortality, CV mortality, all-cause hospitalizations, CV hospitalizations,  
340 HF hospitalization, composite of all-cause mortality or all-cause hospitalization, composite of all-  
341 cause mortality or CV hospitalization, composite of all-cause mortality or HF hospitalization and  
342 composite of cardiovascular mortality or HF hospitalization. All available follow-up will be used with  
343 event rates estimated at 12 months.

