### 344 Tertiary Outcomes Assessed at 9 weeks.

345 The following continuous outcomes will be compared between treatment arms using analysis  
346 of variance adjusting for baseline level of the outcome measure and site: change in CPET duration,

347 change in pVO2 in CPET, change in pVO2%N in CPET, change in 6-MWT distance, change in QoL  
 348 measures with the SF-36 instrument as well as change in depression and anxiety scales. NYHA class  
 349 will be analyzed as ordinal variable using ordinal logistic regression including terms of baseline  
 350 NYHA class, site and treatment arm.  
 351 The summary is included in the **Table 7 and Table 8.**

352 **Table 7. TELEREH-HF Endpoints**  
 353

Primary end-point:
 
The percent of number of days alive and out of hospital (DAOH) during the 12-24 months follow-up

Secondary end-points:
 
Secondary outcomes assessed at 12-24 months:
 
 
- all-cause and CV mortality
 
- all-cause, CV and HF hospitalization
 
 
Tertiary analysis - outcomes assessed at 9 weeks - the effectiveness of hybrid TR based on:
 
 
- New York Heart Association class
 
- cardiopulmonary exercise treadmill test duration
 
- peak oxygen consumption (pVO2)
 
- percentage of predicted peak oxygen consumption (pVO2%N)
 
- six-minute walking test distance
 
- quality of life assessment
 
- depression assessment
 
- anxiety assessment
 
- acceptance of TR
 
- adherence to TR
 

Composite end-points encompasses:
 
 
- CV mortality and HF hospitalization
 
- CV mortality and CV hospitalization
 
- CV mortality and non CV hospitalization
 
- all-cause mortality and CV hospitalization
 
- all-cause mortality and non CV hospitalization
 

354 TRG-telerehabilitation group, CG-control group, CV-cardiovascular, HF-heart failure, TR-telerehabilitation  
 355  
 356  
 357  
 358  
 359  
 360  
 361  
 362  
 363  
 364

365  
 366  
 367  
 368  
 369  
 370  
 371  
 372

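### The primary Wilcoxon test on percent DAOH uses neither site nor baseline prognosis, although site is in the specified secondary and tertiary models; the test is valid, but some precision is left unused

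*Protocol*

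**What the plan says.** **Primary test.** Protocol, Statistical Analyses, Primary Outcome, gives the test for percent DAOH as "up and analyzed using the Wilcoxon-Mann-Whitney test". It names no stratum and no covariate. The section on sample size uses the same test: "Wilcoxon-Mann-Whitney test with the above assumptions and with a sample size of 400 evaluable" patients per arm.

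**Secondary and tertiary models.** The time-to-event outcomes are to be "compared between treatment arms using Cox proportional hazards regression with site and treatment" arm as covariates. The continuous 9-week outcomes are compared by analysis "of variance adjusting for baseline level of the outcome measure and site: change in CPET duration", and so on through the list. NYHA class at 9 weeks is analysed by ordinal logistic regression with baseline class, site and arm.

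**Centre-specific control care.** Under Control Group, patients receive usual "care appropriate for their clinical status and standardized within a particular center (some of them can" take part in rehabilitation, and some have remote monitoring of implanted devices).

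**Baseline data.** Under Clinical examinations, all 850 patients have NYHA class and a cardiopulmonary exercise test, hence peak VO2, at entry.

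**Randomisation.** All five centres use one common web-based allocation process. Stratification by site is not stated.

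**The concern.** The protocol treats site as worth a model term for the secondary and tertiary outcomes, and for the tertiary outcomes it also adjusts for the baseline value. The primary endpoint, on which the trial will be judged, gets neither, and no reason is given.

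One pooled ranking of all patients leaves differences between centres, and differences in prognosis between patients, in the error term. If those sources explain an appreciable part of the variation in DAOH, an adjusted rank test would detect the same treatment effect with higher probability, using data already collected. At stake is power for the primary comparison, not its validity.

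**Working it through.** **Inputs.** All from the protocol's sample size section unless marked:
- Alpha: 0.05, as an "overall two-sided level of significance".
- Allocation: 1:1 ("The sample size for this study is calculated assuming 1:1 treatment allocation ratio").
- Effect: the mean difference for the "TRG arm and the CG arm is 21 days with a common standard deviation in each arm of 100", so 21/100 = 0.21.
- Evaluable patients: 400 per arm.
- Stated power: 80%.
- *Assumption:* the share R² of rank variance explained by site and baseline covariates. The protocol gives no figure, so a range is shown.

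**Step 1: reproduce the stated power.** With asymptotic relative efficiency (ARE) against the t-test, power ≈ Φ(0.21 × √(400 × ARE / 2) − 1.96).
- Normal data, ARE = 3/π = 0.955: 0.21 × √190.99 = 2.902; Φ(0.942) = 82.7%.
- Distribution-free lower bound, ARE = 0.864: 0.21 × √172.8 = 2.760; Φ(0.800) = 78.8%.
- Noether's formula, with P = Φ(0.21/√2) = 0.559 and N = 800: Φ(√2400 × 0.0590 − 1.96) = 82.4%.

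The stated 80% lies inside this range. It belongs to the unadjusted test and is reproduced.

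**Step 2: adjust for site plus baseline covariates.** Replace the variance by its unexplained part: power ≈ Φ(0.21 × √(190.99 / (1 − R²)) − 1.96). The equivalent number of evaluable patients is 800 / (1 − R²).

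| Assumed R² | Power | Equivalent evaluable N |
|---|---|---|
| 0% | 82.7% | 800 |
| 5% | 84.6% | 842 |
| 10% | 86.4% | 889 |
| 15% | 88.3% | 941 |

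**Step 3: site stratification alone.** Simulated with 5 sites, N = 800, normal data, randomisation not stratified by site, and 4,000 runs per row:

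| Assumed site share | Plain Wilcoxon | Site-stratified (van Elteren) |
|---|---|---|
| 0% | 83.0% | 82.6% |
| 1% | 82.9% | 82.5% |
| 2% | 82.8% | 83.4% |
| 5% | 82.6% | 83.7% |
| 10% | 82.4% | 86.5% |

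The Monte Carlo standard error of each figure is about √(0.83 × 0.17 / 4000) = 0.6 point. Up to a 5% share the change is therefore about 0 to 1 point. With randomisation stratified by site, the 5% row becomes 83.5% against 84.6% and the 10% row 82.8% against 85.0%.

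**Step 4: skew and ties.** DAOH is bounded, skewed and tied, so the comparison was repeated on a skewed outcome with roughly 40-50% of patients tied at the maximum. The shape and the latent-scale shares are assumptions; N = 800, 5 sites, 3,000 runs.

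| Site / covariate share | Plain | van Elteren | Site-stratified rank ANCOVA, one covariate |
|---|---|---|---|
| 0% / 0% | 80.6% | 80.7% | 80.1% |
| 2% / 5% | 79.5% | 80.6% | 82.0% |
| 5% / 5% | 81.5% | 82.7% | 84.4% |
| 5% / 10% | 81.4% | 82.6% | 85.4% |
| 10% / 10% | 78.6% | 83.0% | 86.2% |

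In the 5% / 10% row the total gain is 85.4 − 81.4 = 4.0 points, of which site gives 82.6 − 81.4 = 1.2 and the covariate 85.4 − 82.6 = 2.8. With a site share of 5% or less, the covariate gives the larger part in each row. If nothing is explained, the loss is 80.6 − 80.1 = 0.5 point, within simulation error.

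**Step 5: type I error.** On normal data with a 10% site share, the plain test rejected a true null in 5.4% of runs without site-stratified randomisation and in 3.9% with it. The van Elteren test gave about 5.4% and 5.3%. On the skewed outcome all three tests rejected in 4.5-6.0% of runs. Nothing here shows the plain test to be invalid; with site-stratified randomisation it becomes conservative.

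**The case against.** The strongest reply is that nothing is broken. The test named for the analysis is the test used for sizing, it is valid under randomisation, and its null distribution already allows for chance imbalance. Strata and covariates are often settled in a statistical analysis plan. All of this stands except the last remark. This protocol does list model terms for the secondary and tertiary outcomes and lists none for the primary test, so the contrast is in the document itself.

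Several stronger readings are tempting but not supported:
- *That every other comparison adjusts for site.* The section on subgroup and sensitivity analyses states no site term.
- *That baseline risk is adjusted for everywhere else.* The secondary Cox models contain site and arm only. The tertiary models adjust for the baseline of the same measure, and DAOH has no such baseline.
- *That hospital use differs between centres by design.* The Control Group section makes a difference plausible but says nothing of hospital days or of size.
- *That a known amount of power is being lost, for nothing in return.* No variance share is given, and the plain test has the merits of simplicity and of matching the sample size basis.
- *That stratifying by site would secure the whole gain.* Step 3 shows little from site alone unless its share is near 10%.

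It is also fair to say that the study is ongoing and open-label. Changing the primary test is a formal amendment, and its timing must be defensible.

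**Conclusion.** The point holds as one of efficiency and consistency. The primary analysis is unadjusted while the specified secondary and tertiary models carry site, and prognostic variables measured in every patient go unused. A reader might infer that the primary test is invalid or the trial undersized. Neither follows, since the 80% is reproduced and type I error is controlled.

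The likely gain is modest: about 2 points of power if site and covariates together explain 5% of the rank variance, about 4 at 10% and between 5 and 6 at 15%. These figures rest on assumed variance shares and on normal theory. The skewed simulation points the same way, but its outcome shape is also assumed. The case for acting is the asymmetry between a plausible gain of a few points and a loss of about half a point at most.

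**What to change.** Amend the Primary Outcome section before any outcome data are compared by arm, which in an open-label trial is the step that corresponds to unblinding:
- Make the primary test a rank ANCOVA of percent DAOH, stratified by site, with baseline NYHA class and baseline peak VO2 as prespecified covariates.
- State a simple rule for missing baseline values that does not use treatment arm, for example the site median. Few should be missing, since the exercise test is planned at entry for all patients.
- Keep the unstratified Wilcoxon-Mann-Whitney test as a sensitivity analysis.
- Leave alpha and sample size as they are; the present calculation then serves as the unadjusted basis.

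If the sponsor prefers not to change the primary test in an ongoing trial, prespecifying the adjusted test as a supporting analysis would meet the consistency point but would not bring the power gain to the primary comparison.

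The cost is a protocol amendment, a slightly less simple test to explain, the missing-value rule, and about half a point of power at most if the covariates prove uninformative. No new data are needed.

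### The primary endpoint, percent DAOH, is defined on two incompatible windows: the first 365 days and each patient's whole 12-24-month follow-up

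*Protocol*

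**What the plan says.** Two windows appear in the protocol.

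*Whole, variable follow-up.*
- Primary hypothesis sample size considerations: because possible follow-up differs between patients, the primary measure is the "ratio of the DAOH divided by total days of follow-up for each patient".
- Table 7 gives the primary end-point as "The percent of number of days alive and out of hospital (DAOH) during the 12-24 months follow-up".
- The opening sentence of Primary Outcome uses the same 12-24-month period.

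*365 days.*
- The next sentence of Primary Outcome defines DAOH on "the first 365 days of follow-up that the patient was alive minus the total number of days the patient" spent in hospital.
- Missing data applies only to patients on study for under 365 days for reasons other than death. Its first method takes the DAOH proportion over the time the patient "was on study and multiplied by 365".

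For length of follow-up, Primary Outcome starts the ITT period at randomization and has it "extend for a minimum of about 14 months (9 week training period and 12 month follow-up) and a" "maximum of 26 months (9 week training period plus 24 months of follow-up"). The MITT period starts when the 9 weeks end.

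**The concern.** The two windows answer different questions. In the ITT analysis the 365-day window holds the 63 days of the 9-week programme plus the next 302 days (365 − 63). The full window adds everything observed after that.

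If 365 days is meant, the reason given for using a percent falls away, because every patient's planned ITT follow-up exceeds 365 days. If full follow-up is meant, the DAOH definition is wrong, and so are the imputation trigger and multiplier.

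The analyst must therefore choose, and the protocol does not say how. Treatment assignment is open, so a choice made after outcomes by arm can be seen would be open to challenge whichever way it went. A third possibility, 365-day DAOH over total follow-up, is what results if each sentence is applied as it stands.

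**Working it through.** **1. The plan's own figure.** The inputs, all from the sample size section, are a 21-day difference, SD 100, 400 evaluable per arm, two-sided 0.05 and the Wilcoxon-Mann-Whitney test.
- Noether's formula: P(X>Y) = Φ(21/(100√2)) = 0.559. Power = Φ(√(12 × 0.25 × 800) × 0.059 − 1.96) = 82.4%.
- Two-means formula with relative efficiency 3/π: 82.7%. With the lower-bound efficiency 0.864: 78.8%.
- Loss to follow-up: 800/0.95 = 842.1, stated as 842.

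The stated 80% and 842 are adequately reproduced. What is missing is the window to which the 21 and 100 days belong.

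**2. Length of follow-up.** ITT minimum 63 + 365 = 428 days; ITT maximum 63 + 730 = 793 days. MITT: 365 to 730 days.

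**3. Score of an event-free patient followed to administrative end.**

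| Definition | ITT, shortest | ITT, longest | MITT, shortest | MITT, longest |
|---|---|---|---|---|
| 365 days over 365 days | 100% | 100% | 100% | 100% |
| Full over full | 100% | 100% | 100% | 100% |
| Literal join, 365 over full | 365/428 = 85.3% | 365/793 = 46.0% | 365/365 = 100% | 365/730 = 50.0% |

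On the literal join, a patient with 428 days of follow-up would need 365 − 428 × 365/793 = 168 hospital days to score as low as an event-free patient with 793 days. The note to Figure 1 sets a calendar limit of 31/03/2019, which supports the view that follow-up length depends largely on enrolment date.

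**4. Gap in the imputation rules under full follow-up (ITT).** The rules stop at day 365. The uncovered stretch is 428 − 365 = 63 days for the shortest planned follow-up and 793 − 365 = 428 days for the longest.

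**5. Planning difference on the percent scale.** If 21 days and SD 100 are held fixed whatever the window (an assumption):
- 365 days: 21/365 = 5.8 points, SD 100/365 = 27.4 points.
- 428 days: 21/428 = 4.9 points, SD 23.4 points.
- 793 days: 21/793 = 2.6 points, SD 12.6 points.

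**6. Illustrative power.** The protocol gives no mortality, admission rate, length of stay or accrual pattern, so these are all assumptions: 400 per arm, exponential death times, Poisson admissions, mean stay 9 days, ITT follow-up from 428 to 793 days. Ranges cover repeated simulations.

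| Assumed annual mortality; admissions per year (control to TR) | 365/365 | Full/full | Literal, follow-up uniform | Literal, 80% at maximum follow-up |
|---|---|---|---|---|
| 12% to 9%; 0.8 to 0.6 | 86% | 94-95% | 12-17% | about 60% |
| 12% to 7%; 0.8 to 0.65 | 85-87% | 96-97% | 24-28% | about 62% |
| 30% to 18.5%; 0.8 in both | 82-83% | 98% | 65-73% | about 75% |

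A cruder model (normal DAOH, control mean 300, SD 100, difference 21, uniform follow-up) lowers power only from about 84% to about 72% on the literal ratio.

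**The case against.** The strongest reply is that nobody would compute the literal ratio. No sentence writes it out; it arises only when the DAOH definition is put into the ratio in the sample size section. That section uses a percent precisely to remove dependence on length of follow-up, which the hybrid would defeat. This stands. A reader might infer that patients will be ranked mainly by enrolment date, or that power falls to about 12%. The document does not support either as a prediction. Both belong to the least plausible of three versions, and the 12% also needs event rates and a uniform spread of follow-up that are assumed.

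A reader might also infer bias. Follow-up length set by the calendar is unrelated to arm under 1:1 randomization, so the mismatch adds noise.

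Nor is the sample size shown to be wrong. Days are a natural unit under the 365-day definition, and the stated power and total are reproduced.

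The subtracted hospital days carry no limit of their own, but they sit in a sentence about the first 365 days. That is a wording matter, not a separate defect.

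Finally, a statistical analysis plan that is not shown may settle the window. That would not make the protocol consistent: it states two windows for its primary endpoint, which differs from leaving a detail open. The choice among the three listed imputation methods, and any further missing-data scenarios, can properly be left to that plan.

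**Conclusion.** The contradiction holds, and it concerns the primary endpoint. Two consistent versions remain possible, and they are not interchangeable. They cover different periods, and in the illustrations their power is 82-87% for 365 days and 94-98% for full follow-up. Those figures rest on assumed event rates; the existence of two endpoints does not.

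The literal join is a secondary consequence. Its ranges of 85.3% to 46.0% (ITT) and 100% to 50% (MITT) assume no hospital days and follow-up that ends administratively. Its power, about 12% to 75%, depends on assumed event rates and on how follow-up is spread.

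The gap in imputation after day 365 follows directly if full follow-up is the intended window. The point should be settled before outcomes are seen by arm.

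**What to change.** State one window and use it for the numerator, the denominator, the counted hospital days and imputation. Carry it through the sample size section, Primary Outcome, Missing data and Table 7.

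The sponsor's own reason for a percent points to full potential follow-up as primary, meaning planned days from the start of the analysis period to administrative end. In that case:
- rewrite the 365-day sentence in Primary Outcome to refer to that period, counting only hospital days inside it;
- change the imputation trigger and multiplier from 365 to the patient's own potential follow-up, so that loss after day 365 is covered;
- keep 365-day DAOH as a sensitivity analysis, with 365 days in both numerator and denominator;
- state the window to which the 21-day difference and SD of 100 refer, with their percent equivalents.

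If the sponsor prefers 365 days as primary, the sample size section, the opening sentence of Primary Outcome and Table 7 need the matching change.

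The cost is a protocol wording change before database lock. No new data are needed.
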